7.3 Duration of Study

Screening Period:

- 21 days (with the exception of tumor burden assessment (i.e., CT scan), which may be performed within 28 days of dosing

Treatment Period:

- **Part 1 and Part 2 (a-f).** 28-day (± 7 days) cycles until patient discontinuation or withdrawal or study termination (see [Section 10.4](#))

Follow-up Period:

An end of study visit must occur ≥ 30 days after the last dose of PLX9486 and prior to starting any new anti-cancer therapy. A post-study follow-up contact by phone by site staff will be conducted every 3 months during Year 1, then every 6 months thereafter to obtain information on any new anti-cancer therapy received, response, and survival status.

8.0 STUDY POPULATION

Patients must meet the inclusion and exclusion criteria to be enrolled in the study, unless a protocol deviation is granted by the Sponsor.

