8.1 Inclusion Criteria

Each subject must meet all of the following inclusion criteria to be enrolled in the study:

1. Male or female ≥ 18 years old.
2. **Part 1, Part 2b, [REDACTED] and Part 2e:** Patients with advanced solid tumors who have tumor progression following standard therapy, have treatment-refractory disease, or for whom there is no effective standard of therapy.

3. [REDACTED]

4. [REDACTED]

5. Women of child-bearing potential (WOCBP) must have a negative serum pregnancy test at Screening (\leq 7 days prior to the first dose of Study drug) and must agree to use an effective form of contraception from the time of the negative pregnancy test up to 6 months after the last dose of study drug. Effective forms of contraception include abstinence, hormonal contraceptive in conjunction with a barrier method, or a double-barrier method. Women of non-childbearing potential may be included if they are either surgically sterile or have been postmenopausal for \geq 1 year.

WOCBP are defined as females who have experienced menarche, have not undergone successful surgical sterilization (hysterectomy, bilateral tubal ligation, or bilateral oophorectomy), and are not postmenopausal. All females are considered to be WOCBP except if they have been postmenopausal or surgically sterile for \geq 1 year.

6. Fertile men must agree to use an effective method of birth control during the study and for up to 6 months after the last dose of study drug. Male subjects with partners who are either pregnant or become pregnant during the study drug treatment period must agree to continue to use a condom for 90 days after the last dose of study drug.
7. All associated toxicity from previous or concurrent cancer therapy must be resolved (to \leq Grade 1 or Baseline) prior to study treatment administration.
8. Willing and able to provide written informed consent prior to any study related procedures and to comply with all study requirements.
9. Eastern Cooperative Oncology Group (ECOG) Performance Status 0–2.
10. Life expectancy \geq 3 months.
11. Adequate hematologic, hepatic, and renal function:
 - a. Absolute Neutrophil Count (ANC) \geq 1.5 \times 10⁹/L
 - b. Hemoglobin $>$ 8 g/dL
 - c. Platelet count \geq 100 \times 10⁹/L
 - d. AST and ALT \leq upper limit of normal (ULN)

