8.2 Exclusion Criteria

Subjects meeting any of the following exclusion criteria are not to be enrolled in the study to treatment:

1. Known or demonstrated wild type KIT or PDGF-R, or known or demonstrated mutations of PDGF-R, SDH, or NF-1 that are causative for the observed malignancy.
2. For Part 1 (phase 1, single agent): Patients with a known or presumed pathogenic KIT exon 13 or 14 resistance mutation.
3. [REDACTED]
4. Presence of symptomatic or uncontrolled brain or central nervous system metastases. Patients with stable, treated brain metastases are eligible for this trial. However, patients must not have required steroid treatment for their brain metastases within 30 days of Screening.
5. Known or suspected allergy to the investigational agent or any agent given in association with this trial.
6. Clinically significant cardiac disease, defined by any of the following:
 - a. Clinically significant cardiac arrhythmias including bradyarrhythmias and/or the need for anti-arrhythmic therapy (excluding beta blockers or digoxin). (Patients with controlled atrial fibrillation are not excluded.)
 - b. Congenital long QT syndrome or patients taking concomitant medications known to prolong the QT interval except those required for infections that carry a low risk of QTc prolongation. (See [Attachment 4](#) for a list of drugs known to prolong the QT interval and that carry a risk of inducing torsades de pointes.).
 - c. A Fridericia-corrected QT interval of ≥ 450 msec (for males) or ≥ 470 msec (for females) at Screening.
 - d. History of clinically significant cardiac disease or congestive heart failure >New York Heart Association (NYHA) Class II. Patients must not have unstable angina (anginal symptoms at rest) or new-onset angina within the last 3 months or myocardial infarction within the past 6 months.
 - e. Uncontrolled hypertension, defined by a systolic blood pressure > 150 mmHg or a diastolic blood pressure > 100 mmHg that has been confirmed by two successive measurements despite optimal medical management.
 - f. Arterial or venous thrombotic or embolic events such as cerebrovascular accident (including transient ischemic attacks), deep vein thrombosis or pulmonary embolism within the 6 months before start of study drug initiation (except for adequately treated catheter-related venous thrombosis occurring more than 1 month before study drug initiation).

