10.7 Protocol Violations and Deviations

Protocol violations are defined as significant departures from protocol-required processes or procedures that affect patient safety or benefit potential, or confound assessments of safety or clinical activity. A protocol deviation is a departure from the protocol that does not meet the above criteria. Protocol violations or deviations may be grouped into the following categories:

- Enrollment criteria
- Study activities (e.g., missed evaluations or visits, data verification issues)
- Noncompliance with dose or schedule, including dose calculation, administration, interruption, reduction, or delay, or discontinuation criteria
- Investigational product handling, including storage and accountability
- Informed consent and ethical issues

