11.0 STUDY ASSESSMENTS

Event schedules are summarized in [Table 1](#) (Part 1), [Table 2](#) [REDACTED] [Table 3](#) (Part 2b), [Table 4](#) [REDACTED] [Table 5](#) [REDACTED] [Table 6](#) (Part 2e), and [Table 7](#) [REDACTED]

All patients must provide written informed consent. During the consent process, the person obtaining consent must inform the patient of all elements of the study. No protocol-specific procedures, including Screening procedures, are to be performed until the patient has signed and dated an institutional review board (IRB)/independent ethics committee (IEC)-approved informed consent form. The study begins with the signing and dating of the informed consent form.

A patient will be considered enrolled in the study once all inclusion and exclusion criteria have been met, and the completed patient enrollment form has been submitted to Plexxikon Inc., signed by the appropriate representative, and returned to the investigative site.

Screening procedures are to be performed within 21 days before Cycle 1 Day 1 of study therapy. Each treatment cycle for Part 1, [REDACTED] 2b, [REDACTED] 2e, and [REDACTED] will be 28 days.

Dose interruptions in the middle of a treatment cycle will not affect the cycle and day count on the schedule of assessments. For example, if study drug is held on Cycle 1 Day 10, the following day should still be called Cycle 1 Day 11, etc. If a dose interruption occurs at the beginning of a new cycle, then the new cycle and day count will begin when study drug is restarted. For example, if study drug is held at the Cycle 2 Day 1 visit, then the day that the patient does resume dosing will be called Cycle 2 Day 1.

The end of the study for each patient is defined as the date of the last dose of PLX9486, PLX3397, or sunitinib (see [Section 10.4](#) for reasons for discontinuation or withdrawal of a patient from the study).

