14.8 Investigator Compliance

The investigator will conduct the trial in compliance with the protocol provided by Plexxikon, and given approval/favorable opinion by the IRB/IEC and the appropriate regulatory authority(ies). Modifications to the protocol are not be made without agreement of both the investigator and Plexxikon. Changes to the protocol will require written IRB/IEC approval/favorable opinion prior to implementation, except when the modification is needed to eliminate an immediate hazard(s) to subjects. Plexxikon, or a CRO designee, will submit all

protocol modifications to the appropriate regulatory authority(ies) in accordance with the governing regulations.

When immediate deviation from the protocol is required to eliminate an immediate hazard(s) to subjects, the investigator will contact Plexxikon, or a CRO designee, if circumstances permit, to discuss the planned course of action. Any departures from the protocol must be documented.

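### Section 8.0 lets the Sponsor grant eligibility deviations that 8.1, 8.2 and 11.0 do not allow, and a patient admitted that way counts in the 3+3 decision

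*Protocol*

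**What the plan says.** Section 8.0, which introduces the eligibility lists, reads: "Patients must meet the inclusion and exclusion criteria to be enrolled in the study, unless a protocol deviation is granted by the Sponsor". It does not say which criteria may be relaxed, who at the Sponsor decides, on what grounds, or whether an IRB or IEC is involved.

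Three other places state the requirement without exception:

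- Section 8.1: "Each subject must meet all of the following inclusion criteria to be enrolled in the study".
- Section 8.2: "Subjects meeting any of the following exclusion criteria are not to be enrolled in the study to treatment".
- Section 11.0: "A patient will be considered enrolled in the study once all inclusion and exclusion criteria have been met", together with a signed enrollment form.

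Section 10.7 lists "Enrollment criteria" among the categories of violations and deviations. It separates the two: a violation is a significant departure that affects patient safety or potential benefit, or that confounds the safety or activity assessments; a deviation is a departure that does none of these. Section 14.8 adds "Changes to the protocol will require written IRB/IEC approval/favorable opinion prior to implementation", with an exception for immediate hazards, and requires any departure to be documented.

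**The concern.** Read literally, a patient admitted under the 8.0 exception can never satisfy the 11.0 definition of enrolled, and 8.1 and 8.2 bar the same patient. A site cannot follow all four sections at once.

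The statistical interest lies in what happens next. Establishing the RP2D is a primary endpoint of Parts 2b and 2e, and it rests on very small cohorts. If patients outside the criteria can enter those cohorts and be counted, the dose may be set partly in a population that the criteria do not describe. The entry limits also protect patients. The protocol reports severe PLX3397 liver injury, including one fatal case with ongoing cholestatic injury (5.6.1), and sets transaminase and bilirubin limits at entry (8.1).

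**Working it through.** **Step 1. Does any rule remove a waived patient from the count?**

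- Section 9.3 (DLT evaluability): depends on having a DLT, completing Cycle 1 and the number of days dosed. No eligibility condition.
- Section 9.2.2 (escalation and MTD): counts DLTs among evaluable patients, with at least 3 enrolled initially and 0 or 1 of 6 needed to declare the MTD. No eligibility condition.
- Section 12.2 (analysis sets): the modified ITT set needs a dose and any follow-up, the safety set a dose, and the efficacy set a dose and a post-baseline tumor assessment. No eligibility condition.
- Section 10.4 (replacement): allowed after withdrawal for a protocol violation, but only at discretion and only for patients who are withdrawn.

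So a waived patient who completes Cycle 1 or has a DLT is counted.

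**Step 2. Weight of one patient.** 1/3 = 33% of an initial cohort; 1/6 = 16.7% of the 6 needed to declare the MTD.

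**Step 3. Reproduce the plan's own figures.** Tables 27, 29 and 30 give the same escalation probabilities. With true DLT rate p, escalation follows 0 of 3, or 1 of 3 and then 0 of 3:

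P = (1−p)³ + 3p(1−p)² × (1−p)³

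For p = 0.10 to 0.70 this gives 0.906, 0.709, 0.494, 0.309, 0.172, 0.082 and 0.032. All seven agree with the tables (0.91, 0.71, 0.49, 0.31, 0.17, 0.08, 0.03). At p = 0.20: 0.512 + 0.384 × 0.512 = 0.709.

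**Step 4. One waived patient among the first three.** Let that patient's DLT risk be π and everyone else's be p:

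P = (1−π)(1−p)² + [π(1−p)² + 2(1−π)p(1−p)] × (1−p)³

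The protocol gives no DLT rate for ineligible patients, so π is an assumption and is shown over a range.

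At p = 0.20:

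- π = 0.10: 0.576 + 0.352 × 0.512 = 0.756
- π = 0.20: 0.709 (no excess risk, the stated value)
- π = 0.40: 0.613
- π = 0.50: 0.320 + 0.480 × 0.512 = 0.566
- π = 0.60: 0.256 + 0.512 × 0.512 = 0.518

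At p = 0.30, where the stated value is 0.49, the results are 0.587 (π = 0.10), 0.401 (π = 0.50) and 0.354 (π = 0.60).

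Over these values one patient moves the escalation probability by about 5 points (0.756 − 0.709) to 19 points (0.709 − 0.518). The direction depends on whether the waived patient's risk is below or above that of the others.

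**The case against.** The strongest reply is that 8.0 heads the section, so 8.1 and 8.2 can be read as lists governed by its general rule and exception. That is a possible reading of those two. It does not help with 11.0, which stands elsewhere and defines enrollment by all criteria having been met.

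Four stronger readings are tempting, and the documents do not support them.

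- **That the Sponsor may waive any criterion without limit.** Section 8.0 speaks of a deviation. Under 10.7 a departure that affects safety or confounds assessment is a violation, not a deviation. Since 8.0 does not refer to 10.7, the scope is unclear; unlimited scope is not established.
- **That 14.8 forbids the waiver.** Section 14.8 governs changes to the protocol and describes acting "When immediate deviation from the protocol is required to eliminate an immediate hazard(s) to subjects". An exception already written into a reviewed protocol is not plainly a change to it. A case-by-case exception with no ethics step sits awkwardly with 14.8, but the tension is mild.
- **That the party granting waivers alone decides escalation.** Sections 9.2.2, 10.1.1 and 14.4 give that decision to the Sponsor jointly with the investigators. What stands is that 8.0 names only the Sponsor as grantor, its medical monitor or designee approves each enrollment (10.6), and there is no DSMC (14.4).
- **That waivers push the RP2D too high.** A higher-risk waived patient makes escalation less likely. The RP2D also draws on PK and on toxicity beyond the DLT window, and the Part 1 RP2D was chosen on exposure, with 7 patients at that dose (5.5.1.1).

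It is also fair that the synopsis reports one DLT among 49 treated patients, that nothing shows a waiver was ever granted, and that Part 1 is complete. The protocol does not, however, say that enrollment in Parts 2b and 2e is closed, and the 8.0 text is current. Keeping every dosed patient in the safety set is normal practice and is not criticized here.

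**Conclusion.** The point holds as an internal conflict with a real consequence. Section 8.0 permits prospective eligibility deviations that 8.1, 8.2 and above all 11.0 do not, with no process and an unclear scope, and a patient admitted that way enters the 3+3 count. One patient carries 33% of an initial cohort and 17% of an MTD cohort.

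The effect on escalation is illustrative only: 0.76 to 0.52 around the stated 0.71 at a true rate of 20%, assuming one waived patient among the first three with a risk between 10% and 60%. The number of waivers and the true risk of such patients are not given, so no bias in the RP2D can be claimed in either size or direction. No stated figure in the protocol is wrong on this point. The change is worth making because it is cheap and protects both patients and the population in which the dose is set.

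**What to change.** Delete the closing clause of 8.0 that allows a Sponsor-granted deviation, so that it agrees with 8.1, 8.2 and 11.0, and state that no prospective eligibility waivers are given.

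Add how a patient found ineligible after dosing is handled: keep the patient in the safety set, flag the case to the Study Committee, and decide DLT evaluability by a rule fixed in advance that does not depend on whether a DLT occurred. Replacing such patients unless they had a DLT should be avoided, because they would then be counted only when they have events and the observed DLT rate would be biased upward.

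The cost is a few sentences in an amendment, and an occasional near-miss patient who cannot be enrolled.

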8.1 Inclusion Criteria

Each subject must meet all of the following inclusion criteria to be enrolled in the study:

1. Male or female ≥ 18 years old.
2. **Part 1, Part 2b, [REDACTED] and Part 2e:** Patients with advanced solid tumors who have tumor progression following standard therapy, have treatment-refractory disease, or for whom there is no effective standard of therapy.

3. [REDACTED]

4. [REDACTED]

5. Women of child-bearing potential (WOCBP) must have a negative serum pregnancy test at Screening (\leq 7 days prior to the first dose of Study drug) and must agree to use an effective form of contraception from the time of the negative pregnancy test up to 6 months after the last dose of study drug. Effective forms of contraception include abstinence, hormonal contraceptive in conjunction with a barrier method, or a double-barrier method. Women of non-childbearing potential may be included if they are either surgically sterile or have been postmenopausal for \geq 1 year.

WOCBP are defined as females who have experienced menarche, have not undergone successful surgical sterilization (hysterectomy, bilateral tubal ligation, or bilateral oophorectomy), and are not postmenopausal. All females are considered to be WOCBP except if they have been postmenopausal or surgically sterile for \geq 1 year.

6. Fertile men must agree to use an effective method of birth control during the study and for up to 6 months after the last dose of study drug. Male subjects with partners who are either pregnant or become pregnant during the study drug treatment period must agree to continue to use a condom for 90 days after the last dose of study drug.
7. All associated toxicity from previous or concurrent cancer therapy must be resolved (to \leq Grade 1 or Baseline) prior to study treatment administration.
8. Willing and able to provide written informed consent prior to any study related procedures and to comply with all study requirements.
9. Eastern Cooperative Oncology Group (ECOG) Performance Status 0–2.
10. Life expectancy \geq 3 months.
11. Adequate hematologic, hepatic, and renal function:
 - a. Absolute Neutrophil Count (ANC) \geq 1.5 \times 10⁹/L
 - b. Hemoglobin $>$ 8 g/dL
 - c. Platelet count \geq 100 \times 10⁹/L
 - d. AST and ALT \leq upper limit of normal (ULN)
 - e. Total bilirubin and direct bilirubin \leq ULN with an exception of patients with confirmed Gilbert's syndrome. For patients with confirmed Gilbert's syndrome, the total bilirubin should be \leq 1.5 \times ULN.
 - f. Creatinine \leq 1.5 \times ULN or calculated CrCl $>$ 60 mL/min (using Cockcroft-Gault formula)
 - g. PT (INR) \leq 1.5 \times ULN
12. Left ventricular ejection fraction (LVEF) $>$ 50% per ECHO or MUGA for patients on the sunitinib arms (Parts 2e and f).

8.2 Exclusion Criteria

Subjects meeting any of the following exclusion criteria are not to be enrolled in the study to treatment:

1. Known or demonstrated wild type KIT or PDGF-R, or known or demonstrated mutations of PDGF-R, SDH, or NF-1 that are causative for the observed malignancy.
2. For Part 1 (phase 1, single agent): Patients with a known or presumed pathogenic KIT exon 13 or 14 resistance mutation.
3. [REDACTED]
4. Presence of symptomatic or uncontrolled brain or central nervous system metastases. Patients with stable, treated brain metastases are eligible for this trial. However, patients must not have required steroid treatment for their brain metastases within 30 days of Screening.
5. Known or suspected allergy to the investigational agent or any agent given in association with this trial.
6. Clinically significant cardiac disease, defined by any of the following:
 - a. Clinically significant cardiac arrhythmias including bradyarrhythmias and/or the need for anti-arrhythmic therapy (excluding beta blockers or digoxin). (Patients with controlled atrial fibrillation are not excluded.)
 - b. Congenital long QT syndrome or patients taking concomitant medications known to prolong the QT interval except those required for infections that carry a low risk of QTc prolongation. (See [Attachment 4](#) for a list of drugs known to prolong the QT interval and that carry a risk of inducing torsades de pointes.).
 - c. A Fridericia-corrected QT interval of ≥ 450 msec (for males) or ≥ 470 msec (for females) at Screening.
 - d. History of clinically significant cardiac disease or congestive heart failure >New York Heart Association (NYHA) Class II. Patients must not have unstable angina (anginal symptoms at rest) or new-onset angina within the last 3 months or myocardial infarction within the past 6 months.
 - e. Uncontrolled hypertension, defined by a systolic blood pressure > 150 mmHg or a diastolic blood pressure > 100 mmHg that has been confirmed by two successive measurements despite optimal medical management.
 - f. Arterial or venous thrombotic or embolic events such as cerebrovascular accident (including transient ischemic attacks), deep vein thrombosis or pulmonary embolism within the 6 months before start of study drug initiation (except for adequately treated catheter-related venous thrombosis occurring more than 1 month before study drug initiation).

7. Inability to take oral medication or significant nausea and vomiting, malabsorption, external biliary shunt, or significant bowel resection that would preclude adequate absorption.
8. Ongoing infection of \geq Grade 2 severity.
9. Non-healing wound, ulcer, or bone fracture.
10. .Patient has known human immunodeficiency virus (HIV), hepatitis B or hepatitis C infection or is known to be a carrier of hepatitis B or C. Patients who are positive for hepatitis C virus (HCV) antibody must be negative for HCV by polymerase chain reaction (PCR) to be eligible. Prior hepatitis infection that has been treated with highly effective therapy with no evidence of residual infection and with normal liver function (ALT, AST, total and direct bilirubin \leq ULN) is allowed. These patients must be willing to undergo additional testing per local standard of care.
11. Hepatobiliary diseases including biliary tract diseases, autoimmune hepatitis, inflammation, fibrosis, or cirrhosis of liver caused by viral, alcohol, or genetic reasons. Gilbert's disease is allowed if total bilirubin is $\leq 1.5 \times$ ULN.
12. Interstitial lung disease with ongoing signs and symptoms at the time of informed consent.
13. Females who are pregnant or nursing.
14. Any psychological, familial, sociological, or geographical condition that could hamper compliance with the study protocol.
15. Strong CYP3A4 inhibitors or inducers within 14 days or 5 drug half-lives of the agent, whichever is longer, of study drug initiation or the need to continue these drugs during this study. (A list of strong CYP3A4 inhibitors and inducers can be found in [Attachment 2](#).)
16. Major surgery or significant traumatic injury within 14 days of Cycle 1 Day 1.
17. History (within 2 years prior to first study drug administration) of another malignancy unless the malignancy was treated with curative intent and likelihood of relapse is small (<5% in 2 years in the judgment of the investigator). Subjects with a history of squamous or basal cell carcinoma of the skin or carcinoma in situ of the cervix may be enrolled.
18. Anti-cancer therapy within the period immediately before Cycle 1 Day 1:
 - a. Chemotherapy, radiation therapy, small-molecule TKI therapy, or hormonal therapy for the treatment of cancer within 14 days or 5 half-lives (whichever is shorter) of Cycle 1 Day 1.
 - b. Immune therapy or other biologic therapy (other monoclonal antibodies or antibody-drug conjugates) for the treatment of cancer within 28 days of Cycle 1 Day 1.

